Waiver of Informed Consent + Telephone Screening for Study Eligibility

1. WAIVER: Before screening, research team member will obtain telephone consent.
2. SCREENING: After telephone consent is obtained, administer the Telephone Interview for Cognitive Status (TICS). A TICS score of 31 or above is required to participate in the study.
3. Email the participant the consent form via DocuSign.

Intake Interview

1. INTERVIEW: After we receive the informed consent form in DocuSign, participants will be scheduled for their 1-hour intake interview, held on Zoom. All notes collected during the interviews will be entered into a Qualtrics form.

Pre-Test

1. Pre-Test Session #1 (Online):
 - a. Demographic Questionnaire
 - b. Technology Questionnaires
 - c. COVID-19 Questionnaire
 - d. Leisure Activity Scale
 - e. Letter Sets Test
 - f. Personal Beliefs about Memory
 - g. Global Beliefs about Memory
 - h. Word List Free Recall
2. Pre-Test Session #2 (Online):
 - a. Shipley Vocabulary
 - b. Perceived Stress Scale
 - c. Satisfaction with Life Scale
 - d. Memory Functioning Questionnaire
 - e. Memory Compensation Questionnaire
 - f. Personality Questionnaire
 - g. Pattern Comparison
 - h. Verbal Paired Associates

Group Learning Experience + Shaping Calls #1, #2, #3

1. The “Group Learning Experience” (GLE) includes the memory classes. These classes involve a small group of participants (3-6 people) who meet with the trainer to learn the memory strategies.
2. The EMMI and MSC GLEs include four classes (either Mondays/Thursdays or Tuesdays/Fridays) across the span of two weeks. Shaping calls will occur during both weeks of the GLE, plus the week following the conclusion of the GLE.
3. EMMI GLE:
 - o GLE Day 1
 - i. Topics:
 1. Beliefs About Memory
 2. Intentional Encoding
 3. Spaced Retrieval
 - ii. In-Class Activities: N/A

- iii. Homework:
 - 1. HW #1: Belief Restructuring
 - 2. HW #2: New Name Learning
- o GLE Day 2
 - i. Topics:
 - 1. Goal setting and how to do it
 - 2. External Aids
 - 3. Stop Think Plan Act
 - ii. In-Class Activities:
 - 1. Spaced Retrieval
 - 2. Routines and Habits
 - iii. Homework:
 - 1. HW #3: Daily Goal Setting
 - 2. HW #4: External Aids
 - 3. HW #5: Stop/Think/Plan/Act
- o GLE Day 3
 - i. Topics:
 - 1. Implementation Intentions
 - 2. Medications
 - 3. Habits and Routines
 - ii. In-Class Activities:
 - 1. Implementation Intentions
 - iii. Homework:
 - 1. HW #6: Medication Intentions
 - 2. HW #7: Routines and Habits

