Enhancing Older Adult's Everyday Memory Function

Statistical Analysis Plan

NCT #: NCT04088136

12/07/2022

## Statistical Analysis Plan: Study 2

Participants will be randomly assigned to one of two intervention arms: Everyday Memory Metacognitive Intervention (EMMI) and Memory Strategy Control (MSC). The EMMI group is trained in everyday memory skills applicable to self-management of cognitive challenges; the MSC group is trained in mnemonic strategies to form new memories for subsequent memory tests. We are planning to enroll 30 persons in each of the two intervention arms (total N = 60).

We have designated selected primary and secondary outcomes to evaluate. The hypotheses are that (1) EMMI training will improve everyday memory, but not typical memory test performance; and (2) MSC training will improve typical memory test performance but not everyday memory. These hypotheses translate into directional null and alternative hypotheses in standard frequentist statistics. Outcomes are differentiated by whether they are administered at both pretest and posttest or at posttest only. For everyday memory, the posttest-only outcomes include (1) everyday memory failures, or memory slips; (2) laboratory contact task to measure prospective memory, with (a) number of successful calls and (b) timeliness relative to scheduled contact time; and (3) computer simulated tasks assessing complex IADLs, including ATM use and medication management. We predict better performance by the EMMI group at posttest on these measures. The posttest-only cognitive measure is Story Recall, which is seen as a transfer task unlikely to show training benefits, but the directional hypothesis is for better performance in the MSC group.

We estimate the design has a .80 statistical power to detect a standardized mean difference favoring the EMMI group of  $d = 0.64$ ,  $\alpha = .05$ , 1-tailed.

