For outcomes measured at pretest and posttest, we administered several metamemory questionnaires, and designated the following key secondary outcomes: change on MFQ Frequency of Forgetting (a measure of everyday memory complaints), change in PBMI Specific Memory Self-Efficacy and Perceived Control over Memory scales, and change in the Memory Compensation Questionnaire's scales of External Use and Internal Use, assessing use of strategies to support everyday memory. For these measures we hypothesized that the EMMI group would improve in subjective memory more than the MSC group from pretest to posttest. We also administered two memory tests at pretest and posttest, an associative recall test and a free recall test. We hypothesized greater improvement from pretest to posttest for the MSC group who received training in relevant mnemonic strategies that should benefit level of remembering.

Posttest-only analyses will be conducted as independent samples t-tests on key measures with a one-tailed test, according to the direction of the relevant hypotheses. Pretest-Posttest data will be analyzed using Group X Time mixed effects models using SAS PROC MIXED, with repeated measures specified for Time (pretest-posttest).

We also predict that the everyday memory intervention will reduce memory complaints and increase memory self-efficacy and perceived control from pretest to posttest in the EMMI group alone, leading to the prediction of a group (MSC vs. EMMI) X time (pretest, posttest) interaction. Conversely, we predict that memory strategy training in the MSC group will improve memory test performance, leading to the prediction of a group (MSC vs. EMMI) X time (pretest, posttest) interaction. The interaction is a direct analog of a 1 *df* planned comparison for differential gain for the two groups, and hence is also amenable to a directional hypothesis test, halving the critical p-value used for the typical F-test for interaction. We estimate that the design has .80 power to detect these interactions, assuming a training benefit effect size (difference in  $d$ ) of 0.75, 1 tailed (comparable to pretest-posttest associative mnemonic training gains in our lab).

Given that we have selected critical outcome measures and specified a priori hypotheses, no adjustments of critical p-values will be made, especially because we do not wish to sacrifice statistical power for a conservative control over the Type I error rate.

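### The seven pretest-posttest outcomes are tested on raw change; adjusting for the pretest already collected would usually add power and costs almost nothing

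*SAP*

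**What the plan says.** The SAP divides its outcomes by schedule: "Outcomes are differentiated by whether they are administered at both pretest and posttest or at posttest only". Seven are measured twice. Five are questionnaire scales, introduced with "designated the following key secondary outcomes: change on MFQ Frequency of Forgetting" and continuing with two PBMI scales (memory self-efficacy, perceived control) and two Memory Compensation Questionnaire scales (external use, internal use). The other two are memory tests, associative recall and free recall. The protocol's Pre-Test and Post-Test lists confirm both administrations; for example, "d. Memory Functioning Questionnaire" appears in Session #2 of each.

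For these outcomes the SAP says "Pretest-Posttest data will be analyzed using Group X Time mixed effects models using SAS PROC MIXED", with Time as the repeated factor. It calls the interaction a "planned comparison for differential gain for the two groups" and tests it one-tailed. It claims .80 power at an effect of "0.75, 1 tailed (comparable to pretest-posttest associative mnemonic training gains in our lab". It names no pretest covariate, common pretest mean, covariance structure, pretest-posttest correlation or SD unit for the 0.75. It declines multiplicity adjustment partly because "we do not wish to sacrifice statistical power for a conservative control over the Type I error rate".

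**The concern.** In the planned model the pretest enters only as a repeated response, with a free mean in each arm. With two waves and complete data, the interaction is then exactly the difference in mean change. That fixes the pretest slope at 1 whatever the data show. Estimating the slope, or constraining the arms to a common pretest mean, targets the same randomised contrast and uses the same data.

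Power on seven outcomes with 30 people per arm is at stake, in a plan that gives power as a reason for not adjusting alpha. The 0.75 is justified only by earlier gains in associative memory training, and no effect size is offered for the five questionnaire scales. If their effects are smaller, the lost precision matters more. The posttest-only outcomes (memory slips, laboratory contacts, simulated IADLs, Story Recall) are unaffected.

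**Working it through.** **Inputs from the SAP.** 30 per arm; effect 0.75, one-tailed; alpha .05 (stated with the posttest-only power figure); claimed power .80.

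**Assumptions not in the documents.** r = .4 to .8; k = 0.8 to 1.5; complete data; independent participants.

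**1. The SAP's own power figures** (noncentral t, 58 df).
- Posttest-only: d = 0.64 gives .790 (normal approximation .798), so the stated .80 reproduces.
- Interaction: the stated .80 has no unique reproduction, because the SD unit and r are missing. If 0.75 is in change-score SDs, power is .890. If it is in raw-score SDs with k = 1, power of .80 requires r of about .33. At that r, adjusted power is about .915 and the difference detectable with .80 power falls from 0.75 to about 0.62 SD.

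**2. Variance of the two contrasts**, in units of pretest variance, leaving out the common factor 2/n.
- Change: 1 + k² − 2rk.
- Pretest-adjusted, large sample: k²(1 − r²).
- Change minus adjusted: 1 − 2rk + r²k² = (1 − rk)², which cannot be negative. Adjustment is therefore never less precise in large samples, and the gain is nil when rk = 1 (for example r = .8, k = 1.25).
- At k = 1 the ratio adjusted/change is (1 − r²)/(2(1 − r)) = (1 + r)/2.

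Ratio over r = .4 to .8: .54–.64 (k = 0.8), .70–.90 (k = 1), .84–1.00 (k = 1.25), .92–1.00 (k = 1.5). With 60 people, estimating the slope multiplies each by about 1 + 1/56 = 1.018.

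**3. Power if 0.75 is in pretest SDs.** Change test on 58 df; adjusted test on 57 df with the slope-estimation cost included. Entries are change → adjusted.

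| k | r = .4 | r = .5 | r = .6 | r = .7 |
|---|---|---|---|---|
| 0.8 | .890 → .987 | .932 → .993 | .967 → .997 | .990 → 1.00 |
| 1 | .835 → .928 | .890 → .949 | .941 → .972 | .980 → .990 |
| 1.25 | .743 → .799 | .805 → .837 | .873 → .885 | .938 → .938 |
| 1.5 | .641 → .665 | .700 → .707 | .770 → .766 | .849 → .844 |

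**4. Power if 0.75 is in change-score SDs.** The planned test has .890 throughout. Over r = .4 to .8 the adjusted test has .972–.987 (k = 0.8), .912–.960 (k = 1), .885–.928 (k = 1.25) and .885–.906 (k = 1.5).

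**5. A smaller effect.** At an assumed 0.5 pretest SD, k = 1 and r = .5, power goes from .606 to .707.

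**6. Simulation check.** 20,000 runs of the table's cells for k = 1, 1.25 and 1.5 agree to within about .005; at k = 1, r = .4 they give .831 and .929. Type I error is .047–.055 for both tests when participants are independent.

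**The case against.** The planned contrast is valid, fully named and tied to directional hypotheses, so preferring another valid contrast can look like reviewer taste. On the table above, adjustment does not rescue the .80 target. The planned test already reaches .80 in 12 of 16 cells, and the four that fall short go to .799, .665, .707 and .766, the last slightly worse than planned. The largest gains come where power is already ample. The documents do not show which k or r applies to any outcome, and training that spreads out posttest scores would shrink the gain. This all stands as a limit on the size of the benefit. It does not favour fixing the slope at 1: the possible loss is about half a point, the possible gain about ten, and ignorance of r and k is itself a reason to estimate the slope. Outside the table the gain can also cross the target: at r = .3, k = 1, power goes from .783 to .909.

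Three further points stand as conditions.

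- **Training groups.** Training is given in same-arm groups of 3–6 (protocol, Project Overview). With groups of 5, k = 1 and an assumed intraclass correlation of .10, Type I error is .075–.082 for the change test and .081–.085 for the adjusted test. Neither holds .05 if the groups are ignored, and the adjusted test is marginally worse.
- **Timing.** Both documents describe test administration in the past tense, so replacing the deciding contrast now could look data-driven.
- **Added assumption.** Assignment is in Week 1 and pretest in Week 2 (protocol, 7-Week Schedule). A common pretest mean requires that neither knowledge of the arm nor loss between those weeks shifted the pretest scores. The planned model does not impose this.

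**Conclusion.** The concern holds, as a point of efficiency and not of validity. The SAP leaves available precision unused on seven outcomes. The gain is clear if posttest and pretest SDs are similar or the posttest SD is smaller, and small or nil if the posttest SD is clearly larger. Over the assumed grid and both readings of 0.75, the effect on power runs from about +10 points to about −0.5 point. No single figure can be given without r and the SDs, and every power figure here assumes independent participants. The change is worth making because the likely benefit far outweighs the cost and serves the SAP's own stated priority.

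**What to change.** Amend the SAP, with a date, before any analysis by arm:

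1. For each of the seven outcomes, fit PROC MIXED with one pretest mean shared by both arms (terms for time, and for arm at posttest only), an unstructured covariance matrix and Kenward-Roger degrees of freedom.
2. Make the posttest arm difference the one-tailed contrast that decides each outcome. Keep Group × Time as a labelled sensitivity analysis, so that two results per outcome do not leave a choice.
3. Report within-arm change from the same model, so that the prediction of change confined to the EMMI arm can still be shown.
4. State the assumption that neither knowledge of the arm nor loss between Week 1 assignment and Week 2 pretest affected the pretest scores.

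Posttest ANCOVA on the pretest score is an alternative, but it drops anyone missing either score. The protocol's COVID-19 section reports some lost data, and the mixed model keeps people with one score.

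The cost is SAP wording and about 1 df, with no new data; on the grid, at most about half a power point is lost. If analysis by arm has already begun, the adjusted model should be labelled post hoc. Correlation within training groups needs its own provision, whichever contrast is used.

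### The SAP's directional rule for the Group X Time interaction halves the significance threshold instead of the obtained p-value, so as written it is stricter than the ordinary F-test

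*SAP*

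**What the plan says.** The SAP (Statistical Analysis Plan: Study 2) frames its hypotheses as one-sided throughout: "These hypotheses translate into directional null and alternative hypotheses in standard frequentist statistics". For outcomes measured only at posttest it gives a clear rule, "Posttest-only analyses will be conducted as independent samples t-tests on key measures with a one-tailed test", and a matching power statement: "We estimate the design has a .80 statistical power to detect a standardized mean difference favoring the EMMI group of" 0.64, at alpha .05, one-tailed.

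Outcomes measured at both pretest and posttest are analysed by Group X Time mixed models. The SAP describes the interaction as a 1-df "planned comparison for differential gain for the two groups" and adds that it "hence is also amenable to a directional hypothesis test, halving the critical p-value used for the typical F-test for interaction". The next sentence claims .80 power for a difference in d of 0.75 and labels it one-tailed, but gives no alpha, SD unit or pre-post correlation.

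The closing paragraph on multiplicity says "no adjustments of critical p-values will be made, especially because we do not wish to sacrifice statistical power".

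**The concern.** A 1-df F statistic is the square of a t statistic, so its p-value pools both tails. To make the test directional at .05, one checks the sign and halves the p-value obtained; equivalently, the F-test threshold is doubled to .10. The SAP halves the threshold instead, which moves the test the other way.

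The clause covers seven outcomes: MFQ Frequency of Forgetting, two PBMI scales, two Memory Compensation Questionnaire scales, associative recall and free recall. It matters most for the hypothesis that strategy training improves memory test performance. Two of the three tests of that hypothesis are interactions. The third, Story Recall, is a posttest-only measure "which is seen as a transfer task unlikely to show training benefits".

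An analyst who followed the clause exactly would declare some results non-significant that the SAP's one-tailed intent would call significant. An analyst who had to choose a reading after seeing the p-values would be making a choice the plan should already have settled.

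**Working it through.** **Inputs from the SAP.** 30 per arm (N = 60); alpha .05 one-tailed and d = 0.64 for the posttest-only outcomes; a difference in d of 0.75, one-tailed, for the interaction.

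**Assumptions.** Complete data, equal variances and 58 denominator df. With two time points the interaction test is then a two-sample t-test on change scores. The starting threshold of the ordinary F-test is taken as .05, because the SAP states no alpha for the interaction.

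**1. The SAP's own figure.** For the posttest-only comparison, the noncentrality is 0.64 × √(30/2) = 0.64 × 3.873 = 2.479. Against a one-tailed critical t(58) of 1.672, power is .790 (normal approximation .798), which agrees with the stated .80. Two-sided .05 gives .684, which does not. The stated posttest-only power is therefore a one-tailed .05 calculation.

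**2. Thresholds for the interaction.** The smallest significant observed difference in change, in change-SDs, is t × √(2/30) = t/√15 = t/3.873. Power is from the noncentral t at 0.650 change-SDs (noncentrality 0.650 × 3.873 = 2.517), the effect at which the one-tailed .05 test has .80 power.

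| Rule | F-test p needed | Critical F(1,58) | Critical t | Smallest significant difference | Power at 0.650 |
|---|---|---|---|---|---|
| One-tailed .05 (predicted sign) | < .10 | 2.794 | 1.672 | 1.672/3.873 = 0.432 | .800 |
| Ordinary two-sided F-test | < .05 | 4.007 | 2.002 | 2.002/3.873 = 0.517 | .696 |
| Clause as written | < .025 | 5.295 | 2.301 | 2.301/3.873 = 0.594 | .587 |

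With the predicted sign required, the clause as written has a one-sided error rate of .025/2 = .0125. The effect needed for .80 power rises from 0.650 to 0.814 change-SDs.

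**3. Where the verdicts differ.** With the predicted sign, t(58) between 1.672 and 2.301 (F-test p between .10 and .025) is significant under one-tailed .05 and not significant under the literal rule.

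**4. Does the stated interaction power show which rule was meant?** It does not. If 0.75 is in raw-SD units, the effect in change-SDs is 0.75/√(2(1−ρ)), where ρ is the pre-post correlation. Power of .80 is reached at

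- one-tailed .05: ρ = 1 − (0.75/0.650)²/2 = .33;
- literal rule: ρ = 1 − (0.75/0.814)²/2 = .58.

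If 0.75 is already in change-SDs, power is .890 under one-tailed .05, .815 under the ordinary F-test and .726 under the literal rule. The two correlations are back-solved and appear in neither document, so this figure neither supports nor contradicts the clause.

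**The case against.** The best defence is that the intent is plain. The hypotheses are directional, the posttest-only tests are one-tailed, the disputed sentence itself speaks of a directional test, and the next one is labelled one-tailed. On that view the clause is a loose gloss on how to read F-test output. An analyst who simply ran a one-tailed 1-df contrast would be following the plan. An F-test at .025 has no direction and costs power, so it defeats the purpose of its own sentence and is unlikely to be applied.

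Much of this stands. The wording is probably a slip for halving the obtained p-value, and on that reading the analysis loses nothing. Five of the seven outcomes are the metamemory scales that the SAP designates key secondary, and the posttest-only everyday-memory outcomes are untouched. No stated figure is shown to be miscalculated.

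The defence does not rescue the wording. The multiplicity paragraph uses *critical p-values* to mean the significance threshold, so the same term cannot comfortably mean the obtained p-value shortly before. The clause is also the only operational instruction for making the interaction test directional; it carries no sign condition and no alpha. That the intent can be worked out is a reason to state it correctly.

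**Conclusion.** The clause is wrong as written and should be corrected. Taken literally, it replaces a one-tailed .05 test (critical F 2.79) with one stricter than the ordinary F-test (5.29 against 4.01). It raises the smallest significant difference from 0.43 to 0.59 change-SDs and lowers power from .80 to about .59 at 0.65 change-SDs. That also conflicts with the SAP's stated wish to preserve power.

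These losses arise only if the clause is applied literally. They rest on 30 per arm, complete data, 58 df and a starting threshold of .05. The direction of the error does not depend on the sample size. This point does not show that the trial is underpowered.

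**What to change.** Replace the clause with a rule of this form: the one-tailed p-value is half the F-test p-value when the interaction is in the predicted direction, and 1 minus half of it otherwise; it is compared with .05. The sponsor should confirm that the .05 stated for the posttest-only outcomes also applies to the interaction. The predicted direction is already given for each group of outcomes and needs only to be tied to the sign of the contrast.

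The cost is one replaced clause and one confirmation of alpha. Design, data collection and sample size do not change.

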Enhancing Older Adult's Everyday Memory Function

Study Protocol

NCT #: NCT04088136

12/07/2022

RCT PROTOCOL

Project Overview

The Everyday Memory and Metacognitive Intervention (EMMI) is assessed in comparison to an Active Control group (MSC). Participants are randomly assigned to either the EMMI group or MSC group. All participants, regardless of being assigned to the EMMI group versus MSC group, follow the same procedure (outlined below). The only difference between the two groups is the type of memory training the participants receive, which corresponds to the type of shaping calls they receive and the evening surveys they complete.

The intervention was administered in small groups of 3-6 persons all from the same intervention arm (MSC or EMMI). There were four group learning experiences (GLEs), 2 per week for 2 weeks. Individuals viewed PowerPoint presentations given by the interventionist and assistants. These sessions lasted 3 hours and emphasized interaction and group discussion of key points, as well opportunities for participants to share with each other ideas or insights they gained through working on in-class exercises. Participants also completed assigned homework tasks practicing trained skills between each session. Homework was discussed in the next GLE, but was also reviewed in one-on-one shaping calls, in which a member of the team contacted each participant to discuss how they were working with and using the trained techniques, with specific reference to homework exercises.

A key measurement method for the study was using smartphone apps on burner Samsung Galaxy phones that were locked down so as to enable use of the phone only for the research study. Individuals reported on everyday memory experiences via event-based memory problem reporting and an end-of-day diary that recorded reports of memory failures that had occurred that day. The training program for participants required extensive technical support in how to use these burner phones for ecological momentary assessment (EMA).

7-Week Schedule for Each Group of Participants

Task	Week 1	Week 2	Week 3	Week 4	Week 5	Week 6	Week 7
Screening	X						
Informed Consent	X						
Random Assignment	X						
Intake Interview	X						
Pre-Test Sessions		X					
Phone Shipment/Delivery			X				
GLE with Shaping Calls			X	X			
EMA with Shaping Calls					X		
EMA without Shaping Calls						X	
Prospective Memory Call-in Task						X	X
Post-Test Sessions							X
Debrief							X

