 - iv. Provide Prospective Memory Call-in Task Instructions
- o GLE Day 4
 - i. Topics:
 - 1. Smartphone Training
 - 2. Review next steps in study
 - ii. In-Class Activities: N/A
 - iii. Homework: Submit practice Memory Blip Survey

4. MSC GLE:

- o GLE Day 1
 - i. Topics:
 - 1. Beliefs About Memory
 - 2. Intentional Encoding
 - 3. Organizational Strategies
 - ii. In-Class Activities:
 - 1. Categorizable Free Recall Task Version #1
 - iii. Homework:
 - 1. HW #1: Belief Restructuring
 - 2. HW #2: Categorizable Free Recall Task Version #2
- o GLE Day 2
 - i. Topics:
 - 1. Organizational Encoding
 - 2. Associative Encoding/Mediation strategies
 - ii. In-Class Activities: N/A
 - iii. Homework:

- 1. HW #3: Serial Free Recall
- 2. HW #4: Paired Associates
- o GLE Day 3
 - i. Topics:
 - 1. Associative Encoding
 - 2. Self-Testing
 - ii. In-Class Activities:
 - 1. Create paired associates flashcards
 - iii. Homework:
 - 1. HW #5: Self-Testing
 - iv. Provide Prospective Memory Call-in Task Instructions
- o GLE Day 4
 - i. Topics:
 - 1. Distinctiveness
 - 2. Smartphone Training
 - 3. Review next steps in study
 - ii. In-Class Activities:
 - 1. Paired Associates Homework #5 (same word pairs studied during GLE Day 3):
 - iii. Homework: Submit practice Memory Blip Survey
- 5. SHAPING CALLS DURING GLE WEEKS 1 and 2:
 - o WEEK 1: Two shaping calls are held during GLE Week 1 (one call the day after each GLE). During these calls, check-in on homework and ask the participant if they have any questions.
 - o WEEK 2: One shaping call during GLE Week 2 (one call after GLE Day 3). During the call, check-in on homework and questions.
- 6. PROSPECTIVE MEMORY (PM) CALL-IN TASK:
 - o During GLE Day 3 (for both groups), participants are instructed to call the lab two times in Week 6 and two times in Week 7. This task is an assessment of prospective memory. PM Calls should not be scheduled during the participant's Post-Test sessions in Week 7.

16-Day Measurement Period + Shaping Calls #4, #5, #6

1. The day after GLE Day 4, participants will begin the 16-day measurement period. Every day for 16 consecutive days, participants will complete the Morning Survey, Evening Survey (i.e., nightly diary), and blip reports in the Memory Blip Survey (event-based ecological momentary assessment app).

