The original study proposal envisaged group learning sessions to take place on the campus of Georgia Tech, as was done with our original intervention study (Pearman et al., 2020). The pandemic forced us to convert to completely remote assessment, which also required providing technical support to participants in using web-based platforms. All questionnaires, surveys, and cognitive tests were administered via Qualtrics forms, except the proprietary iFunction programs used to simulate everyday complex IADLs. Programs had to be modified to account for computing power and bandwidth issues for some participants, identified in pilot data. Some (but relatively little) data were lost through lost internet connections, program crashes, etc.

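### Does leaving the source of the memory-failure outcome unnamed undermine the SAP's decision not to adjust p-values?

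*SAP*

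**What the plan says.** The SAP sets out its rule in its closing paragraph: "Given that we have selected critical outcome measures and specified a priori hypotheses, no adjustments of critical p-values will be made". The same sentence adds a further ground, that the authors do not want to give up power for strict control of Type I error.

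The SAP's outcome paragraph introduces the everyday-memory measures this way: "the posttest-only outcomes include (1) everyday memory failures, or memory slips". No instrument, score or window follows. The next item, the laboratory contact task, is given its scores: "with (a) number of successful calls and (b) timeliness relative to scheduled contact time".

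The protocol's Project Overview describes event-based problem reporting on a study phone and "an end-of-day diary that recorded reports of memory failures that had occurred that day". The section on the 16-Day Measurement Period has both running together: "Every day for 16 consecutive days, participants will complete the Morning Survey, Evening Survey (i.e., nightly diary), and blip reports". The Project Overview also says that the arms differ in the training received, "which corresponds to the type of shaping calls they receive and the evening surveys they complete".

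**The concern.** The waiver of adjustment rests partly on the measures having been chosen. For memory failures the documents name a construct and leave two instruments open, so that ground is not documented for this outcome. Two analysts could follow the SAP faithfully, one using phone reports and the other the diary, and one might reach significance while the other did not.

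Three features sharpen the worry.

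- **Arm dependence.** The protocol equates the Evening Survey with the nightly diary and says that evening surveys go with the type of training. If the failure items themselves differed by arm, a diary comparison could be biased.
- **Silent days.** With an event-based report, a day without an entry may mean no failure or no reporting.
- **Timing.** Both documents are dated 12/07/2022, and the protocol already looks back on data collection: "Some (but relatively little) data were lost through lost internet connections, program crashes, etc". They do not show that the source was fixed before data existed.

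At stake would be the meaning of a one-tailed .05 result on the outcome listed first under hypothesis 1.

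**Working it through.** **Inputs.** From the SAP: 30 per arm, one-tailed alpha .05, d = 0.64, stated power .80. The correlation between the two sources within an arm is not given, so 0, .3, .5, .7 and .9 are assumed.

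**1. The plan's own figure.** Non-centrality = 0.64 × √(30/2) = 2.479, with df = 58 and critical t = 1.672. Power is .790 by non-central t, or Φ(2.479 − 1.645) = .798 by the normal approximation. The stated .80 reproduces. This is the power for any single score with that effect, whichever source supplies it.

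**2. Error if both sources are tried and the better one reported.** With no true effect, the chance that at least one of two one-tailed .05 tests is significant is 1 − .95² = .0975 at correlation 0. For other correlations it comes from the bivariate normal. The third column also allows a standardised sum of the two sources (simulation, normal approximation).

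| Assumed correlation | Either source | Either source or their sum |
|---|---|---|
| 0 | .098 | .110 |
| .3 | .093 | .100 |
| .5 | .088 | .092 |
| .7 | .080 | .082 |
| .9 | .068 | .069 |

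With one score chosen without sight of the arm comparison, the rate is .05.

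**3. Disagreement between sources.** If both carry d = 0.64, the chance that exactly one is significant is .331, .279, .234, .182 and .104 across the same correlations (simulated t-tests). At correlation 0 this is just 2 × .79 × .21 = .33. It reflects 79% power and would arise for any two fully specified outcomes. It measures significant against non-significant, not effects in opposite directions.

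**4. Splitting alpha.** At .025 per source, critical t = 2.002 and power falls to .684 each. That is the loss the SAP says it wants to avoid.

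**5. Possible bias in the diary.** If arm-specific wording shifted diary reports by an assumed 0.1, 0.2 or 0.3 SD in EMMI's favour with no true effect, the rejection rate would be .10, .19 or .31. The documents describe no such shift, and no p-value adjustment would cure one.

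**6. Window.** The protocol says: "The day after GLE Day 4, participants will begin the 16-day measurement period". Day 4 falls on a Thursday or Friday of Week 4. With Monday-to-Sunday weeks, the 16 days split 3/7/6 or 2/7/7 over Weeks 4, 5 and 6. The schedule table marks EMA only in Weeks 5 and 6, which hold 13 or 14 of the 16 days. The text states the length outright, so the table is most naturally read as a coarse weekly summary.

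**The case for a change.** The strongest case for acting is that the SAP is specific elsewhere. It names individual questionnaire scales and gives two scores for the contact task, so silence on the first-listed outcome stands out. A directional hypothesis does not pick a score, and a wish to keep power does not license choosing between sources after seeing results. Naming one source would take a paragraph and cost no power.

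Much of this stands as description: the source, score and window are not written down. It does not make the plan's rule wrong.

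- The waiver has two grounds, and the power ground is untouched by the choice of source.
- The claim to have selected measures can fairly be read as choosing a few outcomes from a large battery, which the SAP largely does.
- The SAP already tests two scores of the contact task without adjustment and gives no score for the simulated tasks. Fixing one score for memory failures would leave that wider position as it is.
- The timing evidence is mixed. The SAP speaks of randomisation and enrolment in the future tense but of administering questionnaires in the past tense.
- The arm difference in evening surveys may lie in training-specific questions, with common failure items. The documents do not say.
- Phone reports are not clearly the cleaner source. The protocol has staff review them before shaping calls #4 to #6 in the first measurement week, and shaping calls differ by arm. No calls are made in the second week.

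**Conclusion.** No change to the plan follows. This is a missing definition of the kind analysts ordinarily fill: settle on one source, use content common to both arms, take the 16 days the protocol states, and treat the other source as supportive. Done before the arms are compared, that gives the planned one-tailed .05 test at power .79 for d = 0.64.

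The excess error, about .07 to .10 for two sources and up to .11 with a combined score, needs selective reporting that the SAP does not call for. Those figures rest on assumed correlations from .9 down to 0 and normally distributed scores. Bias in the diary is possible but not shown. The consequence is limited further because the prospective-memory contacts, the simulated tasks and the MFQ Frequency of Forgetting scale also address everyday memory. Declining to adjust is an openly stated trade of Type I error control for power, and it does not stand or fall on this one outcome.
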